Clinical Research Protocol: Application of deep learning automation based on
Time-lapse imaging to jointly assess embryo development to improve
pregnancy outcome of single blastocyst transfer

Subject source: the Affiliated Drum Tower Hospital of Nanjing University Medical School

Responsible person: [name]

Department: Reproductive Medicine Department

Contact person: [name]

Contact number: [name]

The research start time: December 30, 2022-June 15, 2024

Version number: AI-2021-01

The date of the document: July 01, 2021

Summary of the case

Project Name	A clinical study based on Time-lapse imaging application of deep learning automated joint evaluation of embryo development to improve the outcome of single blastocyst transplantation pregnancy
Purpose of the study	Based on Time-lapse imaging application of deep learning, this project explores the automatic evaluation model of different developmental stages of embryos, and establishes an automated joint evaluation system for the whole process of embryonic development. In addition, the patients with single blastocyst transplantation are prospectively collected, and the pregnancy outcome of the patients is followed up by TLI+AI evaluation and morphological evaluation, and the pregnancy outcome of the two groups is compared. The project aims to explore key features that play a role in the evaluation of AI embryos to provide a theoretical basis for further screening of high-quality embryos, thereby increasing the implantation rate of single embryo transfer patients, reducing multiple pregnancies and ensuring the safety of mothers and children.
Study Design	This study is an observational prospective study after a retrospective analysis. It is a single-center study without randomization or blindness. In the early stage, 1000 patients are collected from three periods of embryo culture through Time-lapse to establish an automated joint evaluation system for the whole process of embryo development. At the later stage, the patients are divided into two groups: TLI+AI assessment group and morphological assessment group. 100 patients with 5D single blastocyst transplantation are carried out to follow up the pregnancy outcome.

Total number of cases	1000 (retrospective study)+100 (prospective study)

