Case selection	
Criteria for inclusion
 
1) < 40 years of age; 2) Routine IVF cycle; 3) Period number ≤ 2; 4) The number of eggs harvested was 5-15. 5) follicle stimulating hormone (FSH) ≤ 12 IU/L on the third day of menstruation; 6) Patients with more than 3 high-quality embryos per Day 3 and feasible single blastocyst transplantation per Day 5; 7) Patient factors affecting embryo implantation such as endometrial factors.

	
Exclusion criteria
 
1) Preimplantation Genetic Testing (PGT) is needed for male infertility, ovulation cycle and chromosome abnormality.
 
2) Pictures of unformed or non-available blastocysts;
 
3) Incomplete or unclear images were collected during prokaryotic, mitotic and blastocyst phases, which affected the AI evaluation.

Treatment plan	Through conventional ovulation induction and time-lapse culture, the embryo development was observed dynamically, pictures were collected to establish an automated joint evaluation system for the whole process of embryo development, and the embryos were selected for daily 5 single blastocyst transplantation.
Evaluation of curative effect	
Efficacy evaluation indicators (primary efficacy indicators and secondary efficacy indicators)
 
Precision rate, embryo planting rate

	
Safety evaluation index
 
The harmonic mean of accuracy rate and recall rate, abortion rate

Method of statistics	
(1) Statistical analysis of the evaluation system with accuracy and recall rate;
 
(2) χ^2 test was used to compare the rates among control groups, and $p < 0.05$ was considered statistically significant.

Duration of study	December 30, 2022-June 15, 2024

Directory

1. Research background.....	1
2. Research objectives	5
3. Research design types, principles and test procedures	6
4. Case selection.....	8
5. Research methods and technical routes.....	9
6. Observation items and testing time	9
7. Evaluation criteria for curative effect.....	10
8. Observation of adverse events.....	11
9. Quality control and quality assurance of the research	11
10. Data security inspection	11
11.Statistical processing	11
12. Ethics of clinical research.....	12
13. Collection and storage of samples/specimens	12
14. References	12

List of acronyms

English abbreviation	Full English name	Full Chinese name
Assisted Reproductive Technology	ART	Assisted reproductive technology
Single embryo transfer	SET	Single embryo transfer

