3.1 Research design

This study is an observational prospective study. It is a single-center study without randomization or blind grouping. In order to establish an automated joint evaluation system for the whole process of embryo development, it is necessary to collect images of 1000 patients in the prokaryotic, mitotic and blastocyst stages of single blastocyst transplantation in IVF cycles. According to the TLI+AI assessment and morphological assessment, at least 100 cases are required for fresh cycle 5 a Day single blastocyst transplantation. At present, the pregnancy rate of single blastocyst transplantation is basically maintained at 60%. Through this study, the pregnancy rate is expected to be increased to 80%. The test standard α is 0.05.

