3.2 Research steps

(1) Establish an AI-time lapse automated combined embryo evaluation system to improve the accuracy of embryo evaluation

1) According to the entry and expulsion criteria, 1000 patients were enrolled and Time-lapse closed-loop culture embryo images of prokaryotic phase, mitotic phase and blastocyst phase were collected.

2) To establish the inclusion criteria for training samples, screen and sort out embryo picture samples;

3) Five embryologists annotated the image samples to generate training sample sets and test sample sets;

4) Convolutional neural network based on deep learning was used to build the prokaryotic detection network, the splintering period counting network, the splintering period segmentation network and the blastocyst region segmentation network, and train the detection models in each period respectively;

5) The convolutional neural network classification model is built to classify the embryo quality, and the AI-time lapse automatic joint embryo evaluation system is established by using the five-fold crossover method to train and verify the model.

(2) Debug the generalization ability of the model and improve the evaluation function of embryonic development

1) Test the generalization ability of the AI evaluation model by using embryo picture data, and visualize the features dependent on the model classification.

2) Comparative analysis of AI evaluation and manual evaluation, optimization of model with transfer learning method, and improvement of model accuracy.

(3) To verify the automated combined embryo assessment system to improve the pregnancy outcome of single blastocyst transplantation

1) The enrolled subjects undergoing monoblastocyst transplantation were screened, and informed consent was signed with the patients;

2) Routine ovulation, fertilization and embryo culture in time lapse system for dynamic observation;

3) The optimal blastocysts were selected by AI-time lapse system for combined evaluation and manual evaluation, and 100 cases with fresh cycle of 5 blastocysts per Day were prospective performed.

4) The pregnancy outcomes of the two groups, including the implantation rate, abortion rate and the rate of carrying babies home, were followed up for statistical analysis.

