4.2 Inclusion criteria

- 1) < 40 years old;
- 2) Routine IVF cycle;
- 3) Period number ≤ 2 ;
- 4) The number of eggs collected was 5-15;
- 5) $\text{FSH} \leq 12 \text{ IU/L}$ on the third day of menstruation;
- 6) Patients with more than 3 high-quality embryos per Day and feasible 5 single blastocyst transplantation per Day;
- 7) Patient factors affecting embryo implantation such as endometrial factors.

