5.1 Randomization into groups

This study was not a randomized controlled study

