5.6 Study relevant imaging tests

None

6. Observation items and testing time

- 1) The morphological parameters required by the embryos were observed from Day 1-5 during embryo culture;
- 2) Images of prokaryotic stage, cleavage stage and blastocyst stage were collected for the establishment of automated embryo evaluation models at different developmental stages;
- 3) Routine luteal support after embryo transfer, positive blood HCG detected 14 days after transplantation, and pulsation of gestational sac and original cardiac tube detected by B-ultrasound at 4-6 weeks were considered as clinical pregnancy until fetal delivery.

7. Evaluation criteria for curative effect

In this study, deep learning method was used to evaluate the blastocyst quality based on neural network model and manual evaluation of blastocyst quality

In order to improve the accuracy and effectiveness of prediction, the optimal parameter range is adjusted timely according to the results.

The validity evaluation index in the study is the accuracy rate, which represents how many of the predicted positive samples are really positive samples. There are two possible predictions, one is to predict the positive class as positive class (TP), the other is to predict the negative class as positive class (FP), the accuracy rate is $P=TP/(TP+FP)$, the value is not less than 0.9. The safety evaluation index is the harmonic average of accuracy rate and recall rate $F=2*P*R/(R+P)$, that is, positive samples are not expected to be identified as negative samples, or negative samples are identified as positive samples, and the value is not less than 0.9.

In the pregnancy outcome, the clinical results of single embryo transfer were counted, and the data were statistically analyzed by the rate of embryo implantation, the rate of carrying babies home and the abortion rate of safety indicators. The pregnancy rate of single embryo transfer cycle was compared with that of conventional morphology. According to the results, adjust the optimal parameter range in time to improve the accuracy and effectiveness of the prediction.

8. Observation of adverse events

None

9. Quality control and quality assurance of the research (Determine whether this part is needed according to the specific situation of the project)

Embryo culture and transfer within the laboratory are performed in accordance with the standard SOP procedure, and the patient is given full informed consent to improve the subject's compliance.

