11.1 Statistical methods include

Through deep learning method, a 16-layer convolutional neural network structure was built, which was used to extract the features of embryo images in different periods, and then the neural network model was used for statistical analysis. SPSS16.0 software was used for statistical analysis. Through the clinical results of single embryo transfer, the data were statistically analyzed with the embryo implantation rate, abortion rate and baby carrying home rate as indicators. The pregnancy rate of single embryo transfer cycle was compared with that of conventional morphology. According to the results, adjust the optimal parameter range in time to improve the accuracy and effectiveness of the prediction. To obey the normal distribution of measurement data using mean \pm standard deviation ($\bar{x} \pm s$) was described, using samples t test, inspection rate comparing with x^2 . $P < 0.05$ was considered statistically significant.

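### Two non-randomised groups are compared by a crude chi-square, so any difference in patient prognosis is counted as an effect of the AI

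*Protocol*

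**What the plan says.** In the synopsis (Study Design), "the patients are divided into two groups: TLI+AI assessment group and morphological assessment group". Section 3.1 adds: "It is a single-center study without randomization or blind grouping". Section 5.1 repeats that "This study was not a randomized controlled study". No section says how a patient comes to be in one group rather than the other.

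Section 3.2, step (3), sets out what is compared: "The pregnancy outcomes of the two groups, including the implantation rate, abortion rate and the rate of carrying babies home". Section 7 adds that "The pregnancy rate of single embryo transfer cycle was compared with that of conventional morphology", and section 11.1 says the same.

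On the test, the synopsis (Method of statistics) says the chi-square "test was used to compare the rates among control groups", with p < 0.05 as the criterion. Section 11.1 pairs the two tests by data type: "using samples t test, inspection rate comparing with x^2". The t test is for measurement data and the chi-square is for rates. Regression, matching, stratification and propensity scores appear nowhere, and no prognostic covariates are listed.

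**The concern.** Step (3) of section 3.2 is meant to show that AI-assisted selection improves pregnancy outcome. A crude comparison of rates supports that only if the groups would have done equally well without the AI. Randomisation would secure this on average, but here there is neither randomisation nor a stated allocation rule.

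The factors at issue are those settled before a blastocyst is chosen: female age, oocyte number and the Day-3 embryo cohort. Eligibility narrows them but leaves room for the groups to differ. Section 4.2 allows any age under 40, for example, and on oocytes requires only that "The number of eggs collected was 5-15". The t test in section 11.1 might reveal an imbalance in age or oocyte number, but it would not correct the outcome comparison.

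A difference in the quality of the transferred blastocyst is not part of this concern, because that is how the AI is supposed to work.

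If the AI group has the better prognosis, the chi-square can show a benefit that does not exist. If it has the worse prognosis, the test can hide a real one.

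**Working it through.** **Inputs from the protocol.** Pregnancy rate 60% at present and 80% expected with AI, α = 0.05 (sections 3.1 and 11.2); 100 prospective patients (synopsis, sections 3.2 and 4.1).

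**Assumptions.** 50 patients per group, since the split is not stated, with 30 AI / 70 morphology as an alternative; a two-sided Pearson chi-square without continuity correction; and the size of the imbalance, which the protocol does not give. The protocol contains no figure for this bias to reproduce.

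**1. No AI effect, AI group better in prognosis by d points.** The true rates are 60% + d and 60%. The rejection rate is the sum of the binomial probabilities of all outcome pairs for which |z| > 1.96, with z = (p̂₁ − p̂₂) / √[p̄(1 − p̄)(1/n₁ + 1/n₂)].

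| Spurious difference d | 50/50 split | 30/70 split |
|---|---|---|
| 0 points | 5.2% | 5.0% |
| 4 points | 7.1% | 6.5% |
| 8 points | 13.2% | 11.4% |
| 12 points | 24.2% | 20.3% |

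Hand check by normal approximation for d = 8 points, 50/50:
- p̄ = (0.68 + 0.60)/2 = 0.64
- Null standard error: √(0.64 × 0.36 × 2/50) = 0.0960
- True standard error: √(0.68 × 0.32/50 + 0.60 × 0.40/50) = 0.0957
- Upper tail: Φ[(0.08 − 1.96 × 0.0960)/0.0957] = 0.129
- Lower tail: 0.003
- Total: 13.2%, as in the table

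**2. True gain from 60% to 80%, AI group worse in prognosis by d points.** The same enumeration, 50/50, with rates 80% − d and 60%.

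| d | Power |
|---|---|
| 0 points | 59.5% |
| 4 points | 40.3% |
| 8 points | 24.2% |
| 12 points | 13.2% |

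**3. What adjustment recovers.** Simulation with 5,000 replicates, 50/50, no AI effect. One prognostic factor is shifted upwards in the AI group and acts on pregnancy through a logistic model. Group is tested by a Wald test at 1.96, with and without that factor in the model.

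| Shift (SD) | Log-odds ratio per SD | Crude difference | Crude rejection | Adjusted rejection |
|---|---|---|---|---|
| 0.3 | 0.5 | 3.4 points | 6.9% | 4.8% |
| 0.5 | 0.5 | 5.4 points | 8.4% | 5.1% |
| 0.3 | 0.8 | 4.9 points | 8.0% | 5.5% |
| 0.5 | 0.8 | 8.1 points | 13.4% | 4.9% |

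**4. Limit of adjustment.** Add a second, unmeasured factor of equal shift and strength. In the mildest setting (0.3 SD, 0.5) the crude test rejects in 10.2% and the adjusted test in 6.5%. In the strongest (0.5 SD, 0.8) the figures are 31.7% and 11.4%.

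**5. Room for covariates.** At the planning rates the expected number of non-pregnancies is 50 × 0.4 + 50 × 0.2 = 30. Group plus two covariates gives 30/3 = 10 per parameter. Group plus five gives 30/6 = 5, which is thin.

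**The case against.** - **The list of methods may not be exhaustive.** The heading of section 11.1 is open-ended, nothing says the comparison is crude only, and covariate models are often left to an SAP, which is not shown. It is true that the protocol does not forbid adjustment. But chi-square is the only test it names for rates, in two places and with a significance threshold. An SAP that adjusted would contradict the protocol as it stands.
- **The imbalance is assumed.** This stands. Eligibility already restricts age, cycle number, oocyte number, FSH and embryo number, and in the mildest simulated case the harm is small (6.9% against 4.8%). The documents neither support nor exclude an imbalance of 8 to 12 points.
- **The missing allocation rule is the root of the problem.** This also stands. Section 7 could be read as comparing AI-assessed cases with past practice. The 50/50 and 30/70 figures would then not apply, and differences between calendar periods would remain after adjustment for age and embryos. That reading makes the groups less comparable, not more.
- **Adjusting the pregnancy rate chooses an endpoint.** The synopsis lists the implantation rate among its efficacy indicators. However, pregnancy is the rate used for planning and the one that sections 7 and 11.1 compare with conventional morphology. The choice is defensible but should be stated.
- **The protocol openly calls itself observational and non-randomised.** This discloses the limitation but does not change what the test estimates.

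**Conclusion.** The concern holds and should be fixed. The analysis that the protocol names cannot separate an AI benefit from a difference in patient mix. Confidence is high on that point, because it rests on the text alone.

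The amount and direction of bias cannot be derived from the documents. On the assumptions above, a prognostic difference of 4 points does little to the error rate (7.1% at 50/50). A difference of 8 to 12 points raises it to between 13% and 24%, or in the opposite direction cuts power from 60% to between 24% and 13%. Adjustment brings the error rate back to about 5% when the responsible factor is measured, and only part of the way when it is not.

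**What to change.** 1. **Section 5.1:** state how a patient comes to be in each group, and whether the morphology group is concurrent or drawn from past records. The adequacy of any adjustment depends on this.
2. **Section 11.1 and the synopsis:** replace the crude test as the main analysis, for example with:

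> The main comparison is a logistic regression of clinical pregnancy on group, adjusted for female age and number of high-quality Day-3 embryos, graded by the same method in both groups. The adjusted risk difference with its 95% confidence interval is reported.

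3. **Covariates:** settle the model before outcome data are seen, with no more than two or three covariates given about 30 expected non-pregnancies. State in advance when Firth penalisation applies. If oocyte number, FSH and cycle number are also wanted, bring them in through one propensity score rather than as extra terms. Do not adjust for the quality of the transferred blastocyst.
4. **Other outcomes:** keep the crude chi-square as a secondary description. Say that clinical pregnancy is the endpoint of the main comparison, and how the implantation, abortion and take-home-baby rates are handled.
5. **Conclusion:** word it as an association, because only measured confounding is reduced.

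The cost is a few lines of text and a slightly more complex analysis using a few degrees of freedom. Age and embryo number are needed to apply the eligibility criteria, so they are known for every prospectively screened patient. If the morphology group came from past records, they would have to be retrieved. Unmeasured confounding would remain.

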3.1 Research design

This study is an observational prospective study. It is a single-center study without randomization or blind grouping. In order to establish an automated joint evaluation system for the whole process of embryo development, it is necessary to collect images of 1000 patients in the prokaryotic, mitotic and blastocyst stages of single blastocyst transplantation in IVF cycles. According to the TLI+AI assessment and morphological assessment, at least 100 cases are required for fresh cycle 5 a Day single blastocyst transplantation. At present, the pregnancy rate of single blastocyst transplantation is basically maintained at 60%. Through this study, the pregnancy rate is expected to be increased to 80%. The test standard α is 0.05.

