3.4 Study endpoint

Data collection and analysis were completed in 100 prospective 5 Day single blastocyst

transplantation patients

4. Case selection

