11.2 Sample size calculation process

At present, the pregnancy rate of single blastocyst transplantation is basically maintained at 60%. Through this study, the pregnancy rate is expected to be increased to 80%. The test standard α is 0.05.

12. Ethics of clinical research

Clinical research will follow the relevant regulations such as the Declaration of Helsinki of the World Medical Congress. Clinical studies are conducted only after the protocol is approved by the Ethics Committee prior to the start of the study. Before each subject is enrolled in this study, the investigator is responsible to give a complete and comprehensive introduction of the purpose, procedure and possible risks of this study to the subject or his/her agent, and sign a written informed consent. Subjects should be informed that they have the right to withdraw from this study at any time, and informed consent should be kept as a clinical study document for future reference. Subjects' privacy and data confidentiality will be protected during the study.

13. Collection and storage of samples/specimens

In this study, images of embryos were collected every 15 minutes by time-lapse system, and all the images were stored in the computer hard drive. It is stored in the hard disk of the computer of the center. It is backed up regularly every year and kept completely indefinitely.

14. References

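### The 100 prospective cases called required do not fit the 60% to 80% target: as a two-group total they give about 59% power two-sided, and no split reaches 80%

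*Protocol*

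**What the plan says.** Section 3.1 (Research design) says that "at least 100 cases are required for fresh cycle 5 a Day single blastocyst transplantation". The same paragraph puts the current pregnancy rate at 60%, the hoped-for rate at 80% and alpha at 0.05. Section 11.2, which is headed as the sample size calculation, repeats these inputs ("Through this study, the pregnancy rate is expected to be increased to 80%. The test standard α is 0.05") and gives no sample size. Neither section states power, sidedness, allocation ratio or a formula.

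Elsewhere 100 is the entire prospective number:

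- The synopsis gives the total as "1000 (retrospective study)+100 (prospective study").
- Section 3.2, step (3), has "100 cases with fresh cycle of 5 blastocysts per Day were prospective performed".
- Section 3.4 defines the study endpoint as "Data collection and analysis were completed in 100 prospective 5 Day single blastocyst" transplantation patients.
- Section 4.1 also gives 100.

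The comparison is between two groups. The synopsis says "At the later stage, the patients are divided into two groups: TLI+AI assessment group and morphological assessment group", and its statistical methods entry says that a chi-square "test was used to compare the rates among control groups". Section 3.2, step (3), follows up "The pregnancy outcomes of the two groups, including the implantation rate, abortion rate and the rate of carrying babies home". Section 5.1 says that the study is not randomised.

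**The concern.** A number described as required, beside a target difference and an alpha level, reads as the output of a sample size calculation. If 100 covers both groups, these inputs do not lead to it at 80% or 90% power.

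The consequence concerns how the result is read. Suppose the AI system really raises the pregnancy rate from 60% to 80%. A two-sided test with 50 per group would still miss it about 4 times in 10. A reader who has been told that 100 was the number needed could take a non-significant result as evidence of no benefit.

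The document also leaves room for other meanings of 100, and these give very different power.

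**Working it through.** **Inputs.** From sections 3.1 and 11.2: p1 = 0.60, p2 = 0.80, alpha = 0.05. From the synopsis and sections 3.2, 3.4 and 4.1: 100 prospective patients, two groups. Assumed, because the protocol does not say: a 1:1 split, sidedness (both are shown), and 80% and 90% power as benchmarks.

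**The plan's own figure.** There is no calculation to reproduce. The check is whether 100 follows from the inputs.

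**Sample size per group**, pooled-variance formula with mean rate 0.70:

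n = [z_alpha × √(2 × 0.70 × 0.30) + z_power × √(0.60 × 0.40 + 0.80 × 0.20)]² / 0.20²

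The square roots are √0.42 = 0.648 and √0.40 = 0.632.

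| Test | Power | Calculation | n per group | Total |
|---|---|---|---|---|
| Two-sided | 80% | (1.960 × 0.648 + 0.842 × 0.632)² / 0.04 = 81.2 | 82 | 164 |
| Two-sided | 90% | (1.960 × 0.648 + 1.282 × 0.632)² / 0.04 = 108.2 | 109 | 218 |
| One-sided | 80% | (1.645 × 0.648 + 0.842 × 0.632)² / 0.04 = 63.9 | 64 | 128 |
| One-sided | 90% | (1.645 × 0.648 + 1.282 × 0.632)² / 0.04 = 88.03 | 89 | 178 |

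The closest match to 100 is about 70% power one-sided: 49 per group, 98 in total.

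**Power with 50 per group.** Power = Φ[(0.20 × √50 − z_alpha × 0.648) / 0.632].

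- Two-sided: (1.414 − 1.270) / 0.632 = 0.228, so power is 59.0%. Exact enumeration of the uncorrected chi-square test gives 59.5%; with Yates correction it is 51.5%.
- One-sided: (1.414 − 1.066) / 0.632 = 0.551, so power is 70.9%. Exact enumeration gives 72.0%.

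**Does the 1:1 assumption matter?** Two-sided power by normal approximation, with the 60% group listed first: 40/60, 58.7%; 60/40, 55.9%; 20/80, 46.9%; 80/20, 36.9%. A search over all splits from 5/95 to 95/5 gives these maxima:

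| Test | Normal approximation | Exact, uncorrected |
|---|---|---|
| Two-sided | 59.3% (46/54) | 63.5% (45/55) |
| One-sided | 71.0% (48/52) | 73.0% (47/53) |

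No split reaches 80%.

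**What 50 per group can do.** Two-sided power reaches 80% only when p2 is about 0.848, that is, 60% versus about 85%. The expected 95% CI half-width for the risk difference is 1.96 × √(0.24/50 + 0.16/50) = 0.175, or 17.5 percentage points.

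**Other readings of 100.**

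- 100 per group: (0.20 × √100 − 1.270) / 0.632 = 1.154, so power is 87.6% two-sided (88.0% exact). The CI half-width is 1.96 × √(0.24/100 + 0.16/100) = 0.124, or 12.4 points. This contradicts the synopsis total of 100.
- One group of 100 against a fixed 60%, exact binomial with 0.025 in the upper tail: reject at 70 or more pregnancies, power 99.4%. The comparison with conventional morphology in section 11.1 could allow this, but it contradicts the two-group design in the synopsis and section 3.2.

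**The case against.** The strongest objection is that no stated figure is refuted. The protocol gives no power, so 80% and 90% are benchmarks brought from outside, and about 70% one-sided power would give nearly 100. Section 3.1 also does not say that 100 was derived from 60% versus 80%; the statements are only adjacent, in visibly translated English. This stands in part: the finding is not a contradiction of a stated power. But the number is called required beside a target and an alpha level, and at neither conventional power, under either sidedness, does it follow from them.

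Second, section 3.1 says at least 100, which is a floor. However, the synopsis total is a plain 100 and section 3.4 closes the study at 100, so nothing plans for more.

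Third, the readings above are not exhaustive. Comparing the 100 with the 1000 retrospective patients would give about 99% power. That reading is weak: the synopsis divides the later-stage patients themselves into the two groups, and the protocol does not say that pregnancy outcomes exist for the 1000.

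Fourth, the exact maximum of 63.5% comes from an uncorrected test whose true size at that split is somewhat above 5%, so it flatters the design slightly. Leaving it out only strengthens the conclusion.

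**Conclusion.** The concern holds. Read literally, as the total for a two-group comparison, 100 patients give about 59% power two-sided, or 71 to 72% one-sided, for 60% versus 80% at alpha 0.05. The figures quoted assume 50 per group, but the conclusion that 80% is not reached holds for every split. The shortfall at 1:1 against 80% power is 164 − 100 = 64 patients two-sided, or 128 − 100 = 28 one-sided.

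Which meaning of 100 the sponsor intended cannot be settled from the document. The three main readings give about 59%, 88% and 99% power, so the meaning must be fixed before a result can be interpreted. This should be fixed.

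**What to change.** The sponsor should state which reading was meant, and at what power and sidedness, and correct the text to match. No rationale should be added that the sponsor did not have.

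- **100 is the two-group total.** Remove the claim in section 3.1 that 100 is required, and write in 3.1 and 11.2, for example: *With 100 patients in total (assumed 50 per group, two-sided alpha 0.05), power is about 59% for 60% versus 80% and reaches 80% only for about 60% versus 85%. The expected 95% CI half-width for the risk difference is about 17.5 percentage points, so a non-significant result is not evidence of no benefit.* Cost: wording only. No extra patients are needed and power is unchanged, but the plan then shows a less favourable figure.
- **100 per group was meant.** Say so (200 in total, about 88% power two-sided) and reconcile the synopsis and sections 3.2(3), 3.4 and 4.1. Cost: wording in those places and in 3.1 and 11.2, and a commitment to 200 prospective patients.
- **One group against a fixed 60% was meant.** Say so, state that 60% is treated as known, and reconcile the two-group wording in the synopsis and section 3.2(3). Cost: wording there and in 3.1 and 11.2, with no extra patients, but the concurrent comparison group is given up.
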